
2.1 Inclusion/Exclusion Criteria

Inclusion Criteria:

- Age \geq 18 years old AND
- Admitted to cardiology floor (non-ICU) with primary diagnosis of decompensated heart failure AND
- NT-proBNP >1000 ng/L AND
- Initiation of continuous furosemide infusion at a rate of 10mg/hr or higher.

Exclusion Criteria:

- Serum sodium (Na⁺) level less than 120 or greater than 145.
- Average systolic blood pressure >180 mmHg or DBP >100 mmHg over past 24 hours.
- Anticipated length of stay less than 72 hours.
- Use of vasopressin antagonist
- Current use of sodium chloride tablets.
- Active diagnosis of diabetes insipidus
- Inability to tolerate oral diet or swallow pills
- Presence of malabsorptive gastrointestinal disorder (Crohn's disease, short gut syndrome)
- The use of iodinated radiocontrast material in the past 72 hours or anticipated use of intravenous contrast during the current hospitalization
- Admission with intention to undergo open heart surgery.
- Use of intravenous inotropes, vasopressors or vasodilators at enrollment
- A baseline estimated glomerular filtration rate <15 mL/min/1.73m² according to the Chronic Kidney Disease Epidemiology Collaboration (CKD-EPI) formula at the moment of inclusion
- Use of renal replacement therapy at time of enrollment.

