1.0 INTRODUCTION

1.1 Purpose of this Study:

We are proposing a prospective, randomized, double blinded, placebo-controlled single center study evaluating the role of co-administration of oral sodium chloride with intravenous diuretics in patients hospitalized with acute decompensated heart failure. We are approaching this study with the hypothesis that the use of oral sodium chloride leads to improved effective diuresis (as measured by weight loss) and renal function as compared to placebo in patients hospitalized with acute decompensated heart failure undergoing aggressive intravenous diuretic therapy.

Primary endpoint:

[figure not shown]
Our primary outcome will be a composite outcome of change in weight and change in creatinine from baseline to 96 hours (or discharge) after initiation of sodium chloride capsule administration vs placebo (as analyzed by intention to treat)

The bivariate outcome will be displayed on a two-dimensional grid with individual data points for each patient representing paired changes in both creatinine and weight at 96 hours after randomization (or at discharge) (Fig. 1). A confidence region for the average difference between treatment arms in this bivariate response will be described as an ellipse, and the two treatment arms will be compared with the use of the Hotelling T-square test, which is a multivariate analog of the 2-sample t test used with a single continuous variable.

The null hypothesis is that there is no difference between the treatment groups in this 2-dimensional end point.

Secondary endpoints:

- Change in creatinine [timepoint: enrollment to 96 hours (or discharge)],
- Change in weight [timepoint: enrollment to 96 hours (or discharge)]
- Change in daily urine output [timepoint: day of enrollment, active treatment days 1, 2, 3, 4],
- Change in serum sodium [timepoint: day of enrollment, active treatment days 1, 2, 3, 4],
- Change in thirst distress survey [timepoint: enrollment to 96 hours (or discharge), followup phone call],
- Time to discontinuation of intravenous diuretic therapy [timepoint: enrollment to discharge]
- Total diuretic dosage in oral furosemide equivalents [timepoint: enrollment to 96 hours (or discharge)],
- Daily urine output/daily total furosemide dose [timepoint: day of enrollment, active treatment days 1, 2, 3, 4]
- Guideline directed medical therapy [timepoint: enrollment to discharge]

- Total potassium supplementation required [timepoint: enrollment to 96 hours or discharge]

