4.1 Study Evaluations

All study evaluations will be as per clinical standard of care. Research procedures will include the randomization of sodium chloride vs placebo as well as adverse event reporting.

Study Procedures	Time Point 1 Screening/ Enrollment	Time Point 2 Salt vs Placebo Day 1	Time Point 3 Salt vs Placebo Day 2	Time Point 4 Salt vs Placebo Day 3	Time Point 5 Salt vs Placebo Day 4	Time Point 6 Active Treatment Completion Day 5	Time Point 7 Discharge	Time Point 8 Outpatient followup (routine)	Timepoint 9 Followup Phonecall
Informed Consent and Randomization	x								
Collection of baseline characteristics from medical	x								

record (prior medications, PMH, demographics, EF, baseline /admission labs)									
Administer Thirst Distress Survey	x					x			
Vitals and 24 Hour Fluid Balance (Intake/Output)	x	x	x	x	x	x	x	x	
Administration of Salt vs Placebo (2g TID w/ meals)		x	x	x	x				
Collection of Urine electrolytes		x	x	x	x	x	x		
BMP/NT-ProBNP (per usual clinical care)	x	x	x	x	x	x	x	x	
Review of Current Medications and Diet Order	x	x	x	x	x	x	x	x	
Blood draw for biomarker analysis*		x				x			
Adverse Events		x	x	x	x	x	x	x	x
Reason for discontinuation of study drug			x	x	x	x			
Length of hospital stay							x		
Phone Contact Readmission?									x

* Blood draws for biomarker analysis will be limited to the first 50 patients enrolled.

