5.0 Statistical Analysis and Endpoints

5.1 Sample Size and Primary Endpoint:

Population: Acutely decompensated heart failure patients with or at risk for diuretic resistance or congestive nephropathy.

Hypothesis: Use of oral sodium chloride will lead to increased fluid volume removal and attenuate diuretic related renal dysfunction.

Study Design: Prospective, randomized, double blind, placebo controlled, single-center study

Endpoint: Net change in weight and change in creatinine from baseline to 96 hours after initiation of sodium chloride capsule supplementation [or discharge] vs placebo (as analyzed by intention to treat)

Power: 80% (2-sided alpha 0.05)

Sample Size Estimate: 85

Trial	Endpoint	SD	alpha	Power	Difference	Sample size
UNLOAD	Wt change (kg)	3.5	0.5	80	2.2	80
DOSE	Wt change (kg)	4	0.5	80	2.2	104
CARESS-HF	Wt change (kg)	5.1	0.5	80	2.2	168
ATHENA-HF	Wt change (kg)	3.4	0.5	80	2.2	74
Aliti	Wt change (kg)	2.85	0.5	80	2.2	52
3T	Wt change (kg)	2.7	0.5	80	2.2	48
AVERAGE		3.77	0.5	80	2.2	84
<hr/>						
UNLOAD	Cr change (mg/dl)	0.6	0.5	80	0.3	126
CARESS-HF	Cr change (mg/dl)	0.53	0.5	80	0.3	98
Athena-HF	Cr change (mg/dl)	0.3	0.5	80	0.3	32
AVERAGE		0.476	0.5	80	0.3	80

Based on data from the above clinical trials which evaluated diuretic strategies in decompensated heart failure, we believe that 85 patients will give us 80% power to detect a 2.2 kg (5 lb) difference in weight and a 0.3mg/dl difference in serum creatinine levels at 96 hours.

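### The follow-up thirst survey and second biomarker draw are scheduled only at Day 5, although the entry rule admits patients expected to go home before then

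*Combined protocol and SAP*

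**What the plan says.** Section 2.1 lists among the exclusions an "Anticipated length of stay less than 72 hours". It does not say whether the stay counts from admission, enrollment or first capsule.

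The primary endpoint in section 1.1 is the change in weight together with the "change in creatinine from baseline to 96 hours (or discharge) after initiation of sodium chloride capsule administration vs placebo", and section 5.1 defines it in the same way. Both therefore allow a discharge reading.

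In the schedule of section 4.1, the last dosing column is "Time Point 5 Salt vs Placebo Day 4", followed by a Day 5 column for completion of treatment and then separate columns for Discharge, outpatient follow-up and the phone call. The row "Administer Thirst Distress Survey" has two marks, at Enrollment and at Day 5. The biomarker row also has two, at Day 1 and at Day 5, and a footnote limits it to the first 50 patients.

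The secondary endpoint list in section 1.1 times the thirst change from enrollment to 96 hours or discharge and adds the follow-up phone call. Length of the index hospitalization is in the same list, timed from enrollment.

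**The concern.** The entry floor is one day shorter than the treatment course, so some eligible patients are expected to leave before the Day 5 column applies to them. For the primary endpoint this was foreseen. For thirst and biomarkers the schedule offers no other occasion for a second measurement.

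Two things are at stake. The first is a conflict between the endpoint definition and the schedule that staff will work from: the thirst endpoint calls for a discharge reading and a phone-call reading, and the table prompts neither. The second is the kind of missing data that results. Discharge happens after randomization, and the trial itself treats length of stay as an outcome that treatment might change. If a value exists only for patients still in hospital on Day 5, the comparison is made in a subset defined after randomization, and the two arms may not be selected in the same way.

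**Working it through.** **1. Size of the gap.** The entry floor is 72 h (section 2.1) and the endpoint time is 96 h (sections 1.1 and 5.1): 96 − 72 = 24 h, one of four dosing days. Three administrations a day for four days make 12; a patient who leaves after three days has had 9, and 9/12 = 75%.

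**2. Start of the count.** If the stay counts from enrollment, the gap is 24 h. If it counts from admission, the gap can be wider: a patient enrolled 48 h after admission with an expected total stay of 80 h passes the criterion with 80 − 48 = 32 h left. Section 1.1 times length of hospitalization from enrollment, while section 7.1.1 collects admission and discharge dates and a hospital stay in days. Either reading is open. The 96-hour clock is not uniform either: it starts at the first capsule in the endpoint definitions, but the description of the bivariate plot in section 1.1 has "paired changes in both creatinine and weight at 96 hours after randomization (or at discharge".

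**3. Marks in the schedule, set against the endpoint definitions.**

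| Assessment | Baseline | Day 5 | Discharge | Phone call | Timing in section 1.1 |
|---|---|---|---|---|---|
| Chemistry (creatinine) | yes | yes | yes | no | 96 h or discharge |
| Thirst survey | yes | yes | **no** | **no** | 96 h or discharge, and phone call |
| Biomarker draw | Day 1 | yes | **no** | no | not a listed endpoint |

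Vitals, fluid balance and urine electrolytes are also marked at Discharge, so that column is in use and is not implied by Day 5. Section 7.1.1 lists only readmission and adverse events for the phone call, which agrees with the table and not with the thirst endpoint.

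**4. Values lost.** If a share q of patients leaves before Day 5 and the table is followed, the loss is 85 × q thirst values and, among the first 50 patients, 50 × q biomarker values. The documents give no q, so the range is assumed.

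| q | Thirst (of 85) | Biomarker (of 50) |
|---|---|---|
| 10% | 8.5 | 5 |
| 30% | 25.5 | 15 |
| 50% | 42.5 | 25 |

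**5. Does the gap also undermine the primary power?** First the plan's own figure, with per-arm n = 2(1.960 + 0.842)² SD²/δ², two-sided alpha 0.05 as in the power line (the table column prints 0.5), and 1:1 allocation assumed.

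- Weight: the six listed SDs average 21.55/6 = 3.59, which gives 41.8, so 42 per arm and 84 in total, as printed. The printed average SD of 3.77 gives 46.1, so 94 in total; that is a separate matter.
- Creatinine: SD 0.476 and δ = 0.3 give 39.5, so 40 per arm and 80 in total, as printed.

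Now assume that 25% of patients are read at 72 h with 75% of the effect. The mean weight difference is 2.2 × (1 − 0.25 × 0.25) = 2.06 kg. With 42.5 per arm and SD 3.59, power on weight alone, Φ(δ/(SD√(2/42.5)) − 1.96), goes from 80.6% to 75.4%.

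The planned primary test is the bivariate Hotelling T-square. Its noncentrality is λ = (42.5/2)(D₁² − 2ρD₁D₂ + D₂²)/(1 − ρ²), with D₁ = 2.2/3.77 = 0.584 and D₂ = 0.3/0.476 = 0.630, referred to F with 2 and 82 degrees of freedom. The correlation ρ is not in the documents.

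| Assumed ρ | All read at 96 h | 25% read at 72 h | 25% read at 48 h (half the effect) |
|---|---|---|---|
| −0.3 | 99.0% | 98.0% | 96.2% |
| 0 | 94.6% | 91.4% | 87.1% |
| +0.3 | 87.3% | 82.5% | 76.6% |
| +0.5 | 82.0% | 76.5% | 70.2% |

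The direction is a loss, but whether power passes below 80% depends on inputs that the documents do not supply.

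**The case against.** The strongest defense is that the plan foresaw early discharge. Every statement of the primary endpoint allows a discharge reading, the analysis is by intention to treat, chemistry is taken daily and at discharge, and reasons for stopping study drug are recorded. A 72-hour floor secures most of the course without confining the trial to longer-stay patients. This stands, and it makes the threshold a defensible design choice.

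On thirst, one can add that the endpoint definition already calls for a discharge reading, so the absent mark is a clerical gap that staff might fill. That is fair as to its gravity. It does not remove the conflict, because the schedule is what prompts the assessment. The biomarker draw has no such fallback, although it concerns only 50 patients and is not a listed endpoint.

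A reader might infer three stronger things that the documents do not support:

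- **That the trial knowingly enrolls patients who cannot complete the course.** The criterion rests on a forecast of stay, which can be exceeded, and nothing in the text shows intent.
- **That power falls below the stated 80%.** The weight-only figures are illustrative. They rest on an assumed share and on linear build-up of the effect, and weight alone is not the primary test.
- **That the patients lost would be the best responders.** This is plausible, but nothing in the documents says so.

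**Conclusion.** The point holds as a conflict between schedule and endpoint definition. Eligible patients who are discharged before Day 5 have, if the table is followed, no second thirst or biomarker value. For thirst this contradicts section 1.1 twice, at discharge and at the phone call. That conclusion needs no numerical assumption, only the position of the marks in the table.

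The number of patients affected is unknown and scales directly with the share discharged before Day 5. The possible bias rests on one further premise, that treatment may affect discharge timing; the plan allows for this by making length of stay an outcome. The primary endpoint is not missing for these patients, and no shortfall in its power is established. The unstated start of the 72-hour count is a real ambiguity, because it decides how far short of Day 5 an eligible patient may be expected to fall.

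**What to change.** In the section 4.1 schedule, require the thirst survey, and the second biomarker draw for the first 50 patients, at Day 5 or at discharge if that comes first. Add a thirst mark at the follow-up phone call, and add thirst to the phone-call items in section 7.1.1, so that both match section 1.1.

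In section 2.1, state that the 72 hours are remaining stay, counted from enrollment or from the first capsule, and use one origin for the 96-hour clock throughout. Add a sentence on how the 72-hour criterion, the four-day course and the reading at 96 hours or discharge fit together. The threshold itself is for the investigators to justify; no other value is proposed here.

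The cost is a few schedule marks and two or three sentences. Some assessments move to the day of discharge, so their timing will vary slightly; recording the actual date and time of each would let the analysis describe this.

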3.0 Study Procedures

Prior to the initiation of participation, a signed and dated informed consent and permission to use protected health information must be obtained. Randomization will occur via REDCAP Randomization Tool

4.1 Study Evaluations

All study evaluations will be as per clinical standard of care. Research procedures will include the randomization of sodium chloride vs placebo as well as adverse event reporting.

Study Procedures	Time Point 1 Screening/ Enrollment	Time Point 2 Salt vs Placebo Day 1	Time Point 3 Salt vs Placebo Day 2	Time Point 4 Salt vs Placebo Day 3	Time Point 5 Salt vs Placebo Day 4	Time Point 6 Active Treatment Completion Day 5	Time Point 7 Discharge	Time Point 8 Outpatient followup (routine)	Timepoint 9 Followup Phonecall
Informed Consent and Randomization	x								
Collection of baseline characteristics from medical	x								

record (prior medications, PMH, demographics, EF, baseline /admission labs)									
Administer Thirst Distress Survey	x					x			
Vitals and 24 Hour Fluid Balance (Intake/Output)	x	x	x	x	x	x	x	x	
Administration of Salt vs Placebo (2g TID w/ meals)		x	x	x	x				
Collection of Urine electrolytes		x	x	x	x	x	x		
BMP/NT-ProBNP (per usual clinical care)	x	x	x	x	x	x	x	x	
Review of Current Medications and Diet Order	x	x	x	x	x	x	x	x	
Blood draw for biomarker analysis*		x				x			
Adverse Events		x	x	x	x	x	x	x	x
Reason for discontinuation of study drug			x	x	x	x			
Length of hospital stay							x		
Phone Contact Readmission?									x

* Blood draws for biomarker analysis will be limited to the first 50 patients enrolled.

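### The schedule omits the thirst endpoint's discharge and phone-call timepoints, so staff who follow it would collect no post-baseline score from patients discharged before Day 5

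*Combined protocol and SAP*

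**What the plan says.** Section 1.1 lists among the secondary endpoints "Change in thirst distress survey [timepoint: enrollment to 96 hours (or discharge), followup phone call". The endpoint therefore has a treatment-period value, taken at 96 hours or at discharge, and a later value by telephone.

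The schedule in section 4.1 has nine time points. The row "Administer Thirst Distress Survey" is marked at Time Point 1 (screening/enrollment) and Time Point 6 (Day 5). It is blank at Time Point 7 (discharge), Time Point 8 (routine outpatient follow-up) and Timepoint 9 (phone call).

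Two other places show that discharge before Day 5 is anticipated. The primary outcome in section 1.1 is "change in weight and change in creatinine from baseline to 96 hours (or discharge) after initiation of sodium chloride capsule administration". The relevant exclusion in section 2.1 is "Anticipated length of stay less than 72 hours", so a patient expected to stay between 72 and 96 hours can be enrolled.

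Section 5.4 (Analytical Plan) only refers back to the preceding text, and no rule for missing data is given anywhere.

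**The concern.** The endpoint definition and the schedule tell staff to do different things. Coordinators usually work from the schedule. If they do so here, a patient who goes home before Day 5 answers the survey once, at enrollment, and has no change score.

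Weight and creatinine are less exposed. The rows for vitals with fluid balance and for BMP/NT-proBNP are marked at discharge, and such values may also be found in the chart. A patient's own rating of thirst on the day of leaving cannot be reconstructed afterwards.

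Whether a score is missing would depend on time to discharge, which is determined after randomization. Length of the index hospitalization is itself a secondary endpoint, and the rationale in section 1.2 cites a hypertonic saline trial that reported shorter stays. If the capsules change length of stay, the proportion without a score would differ between arms, and the thirst comparison would be made in a subset selected after randomization.

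**Working it through.** **1. Is the blank cell real?** The table was read from a PDF, so the column alignment has to be checked. Rows whose correct position is obvious serve as controls.

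| Row in section 4.1 | Columns marked |
|---|---|
| Thirst survey | 1, 6 |
| Urine electrolytes (control) | 2 to 7 |
| Length of hospital stay (control) | 7 |
| Phone contact on readmission (control) | 9 |

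Length of stay falls under discharge and the phone contact under the phone call, as they should. The columns are aligned, and the blanks at 7 and 9 in the thirst row are what the table says.

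**2. Could the Day 5 column stand for discharge?** Its label is "Time Point 6 Active Treatment Completion Day 5", and discharge has its own column. Vitals, urine electrolytes, BMP/NT-proBNP and medication review are marked in both, so the table treats them as separate occasions.

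**3. Endpoint and schedule side by side.**

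| Timepoint | Section 1.1 endpoint | Section 4.1 schedule |
|---|---|---|
| Enrollment | yes | marked |
| 96 hours (Day 5) | yes | marked |
| Discharge, as the alternative to 96 hours | yes | blank |
| Follow-up phone call | yes | blank |

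The variables listed in section 7.1.1 for the 30+ day call are readmission and adverse events, so that list does not supply the telephone score either. Under the schedule, a patient discharged before Day 5 has no post-baseline thirst survey.

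**4. Size.** The plan states no figure for this, so there is none to reproduce. The planned number is "Sample Size Estimate: 85" (section 5.1). The proportion m discharged before Day 5 is not given and is assumed here. The number without a change score is 85 × m, and the number with one is 85 × (1 − m). With complete data on 85 as the reference, the standard error of the comparison grows by a factor of about 1/√(1 − m).

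| Assumed m | Without score | With score | Standard-error factor |
|---|---|---|---|
| 5% | 85 × 0.05 = 4.25 | 80.75 | 1/√0.95 = 1.026 |
| 10% | 85 × 0.10 = 8.5 | 76.5 | 1/√0.90 = 1.054 |
| 20% | 85 × 0.20 = 17 | 68 | 1/√0.80 = 1.118 |
| 30% | 85 × 0.30 = 25.5 | 59.5 | 1/√0.70 = 1.195 |

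This gives about 4 to 26 patients without a change score. The loss of precision runs from slight to moderate. The selection described above is the more serious issue, and it cannot be sized from the documents.

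**The case against.** **The loss is not certain.** Section 1.1 itself calls for a measurement at discharge and another by phone. Staff who follow it would collect both, and the REDCap data dictionary mentioned in section 7.1.1, which is not part of these documents, may carry them. This stands. The documents conflict and do not settle that the scores will be lost. What they do show is that the table, read as written, does not ask for them.

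**Early discharge may be uncommon.** Patients must be on a continuous furosemide infusion of at least 10 mg/hr, and short anticipated stays are excluded, which points towards longer stays. The exclusion also does not say when its 72 hours begin. This stands as a caution on size. The range therefore starts at 5%, and no value within it is documented.

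**Thirst has no special rank.** It is one of 15 unranked secondary endpoints. A reader might take it for a main outcome because the rationale mentions thirst under sodium restriction, but no section gives it priority. The gap does not touch the primary endpoint.

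**Who leaves early.** A reader might infer that early leavers are the patients who decongest fastest. The documents do not say so. Missingness that differs by arm is a possibility that depends on treatment affecting length of stay.

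**The biomarker draw.** The row "Blood draw for biomarker analysis" is also blank at discharge, with marks at Day 1 and Day 5, and a reader might infer the same contradiction. The documents do not support that. No biomarker endpoint is listed, and the footnote says "Blood draws for biomarker analysis will be limited to the first 50 patients enrolled". A fixed Day 1 and Day 5 pair conflicts with nothing stated, and adding discharge samples would mix different lengths of treatment. It is not part of this point.

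**Conclusion.** The point holds as an inconsistency between the thirst endpoint in section 1.1 and the thirst row of the schedule in section 4.1. The schedule carries neither the discharge alternative nor the phone-call timepoint. Followed as written, it yields no post-baseline thirst score for anyone discharged before Day 5, a group the plan foresees.

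Confidence is high in the pattern of marks and the mismatch, and lower in the consequence. The figure of about 4 to 26 of 85 patients rests on an assumed 5% to 30% early-discharge rate and on staff following the table over the endpoint text. Bias between arms further requires an effect of treatment on length of stay. The point should be corrected because the lost data could not be recovered and the remedy costs almost nothing.

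**What to change.** In the thirst row of the section 4.1 schedule, mark the survey as *Day 5 or at discharge, whichever is first*, with a mark under Time Point 7 that applies only to patients leaving before Day 5. In the same edit, settle the phone call: either mark the survey at Timepoint 9 and add it to the phone-call variables in section 7.1.1, or remove that timepoint from the endpoint in section 1.1. Without this second step the table and the endpoint would still disagree.

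The discharge change is a one-row edit and gives no patient more in-hospital surveys than already planned. Staff must reach early leavers before they go. Keeping the telephone timepoint adds the survey to a call that is already scheduled; dropping it adds nothing.
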